**(CHOOSE ALL THAT APPLY)**

- a. Smoke cigarettes
- b. Smoke cigars, cigarillos, or little cigars
- c. Use chewing tobacco, snuff, or dip
- d. Use electronic cigarettes or e-cigarettes
- e. Smoke tobacco from a hookah or waterpipe
- f. Smoke pipes filled with tobacco (not waterpipe)
- g. Use snus
- h. Use dissolvable tobacco products
- i. Smoke bidis (small brown cigarettes wrapped in a leaf)
- j. No one who lives with me now uses any form of tobacco

4. How old are you?

- a. 11 years old
- b. 12 years old
- c. 13 years old
- d. 14 years old
- e. 15 years old
- f. 16 years old
- g. 17 years old

5. What is your sex?

- a. Male
- b. Female
- c. Don't know, or something else

6. What grade are you in?

- a. 5th
- b. 6th
- c. 7th
- d. 8th
- e. 9th
- f. 10th
- g. 11th
- h. 12th
- i. Ungraded or other grade
- j. In college/university

7. Are you Hispanic, Latino/a, or Spanish origin (One or more categories may be selected)?

- a. No, not of Hispanic, Latino/a, or Spanish origin
- b. Yes, Mexican, Mexican American, Chicano, or Chicana
- c. Yes, Puerto Rican
- d. Yes, Cuban
- e. Yes, Another Hispanic, Latino/a, or Spanish origin

8. What race or races do you consider yourself to be?  
**(You can CHOOSE ONE ANSWER or MORE THAN ONE ANSWER)**
- a. American Indian or Alaska Native
  - b. Asian
  - c. Black or African American
  - d. Native Hawaiian or Other Pacific Islander
  - e. White

9. Please provide email address if you would like a \$5 electronic Amazon gift card.

---

10. Please provide address if you would like a \$5 electronic Amazon gift card.

---

**Appendix D. Parent Brief Questionnaire (PBQ)**

1. As far as you know, has your child ever smoked a cigarette or used other tobacco products, such as e-cigarettes, cigars, a pipe, a hookah, smokeless tobacco, dissolvable tobacco, bidis, or kreteks? Please look at this list. Would you say...
  - a. You know that s/he has
  - b. You strongly suspect that s/he has
  - c. You don't think s/he has or
  - d. You are confident s/he has not
  
2. Do you think cigarettes or tobacco might be available to your child at your home?
  1. Yes
  2. No
3. In the past 30 days, have you smoked a cigarette, a cigar, a pipe, even one or two puffs?
  - a. Yes
  - b. No
  
4. In the past 30 days, have you used smokeless tobacco, such as chewing tobacco, snuff, snus, or dip, even one or two times?  
[Do not include e-cigarettes or products such as a nicotine patch, gum, inhaler, nasal spray, lozenge, or pill]
  - a. Yes
  - b. No
  
5. In the past 30 days, have you used e-cigarettes, a hookah, or dissolvable tobacco, even one or two times?
  - a. Yes
  - b. No

**Appendix E. Pediatric Primary Care Tobacco/Nicotine Best Practices Screening Tool**

*(Response options: Met? Yes or No)*

**Best Practice:**

1. Documentation that youth was asked about current use of:
  - a. Cigarettes
  - b. Cigars/Cigarillos
  - c. E-cigarettes
  - d. Hookah
  - e. Smokeless tobacco products
2. If youth smokes or uses nicotine products, was youth asked about amount used (e.g., just a puff, 5 cigarettes a day and so on)?
3. If youth smokes or uses nicotine products, was youth asked about how often used (e.g., daily, monthly and so on)?
4. Was youth asked if he/she anticipated using cigarettes or nicotine products in the future?
5. Was youth advised to not use: Cigarettes, Cigars/cigarillos, E-cigarettes, Hookah, or Smokeless tobacco products
6. For those who smoke or use tobacco products was youth asked if they were ready to quit?
7. For those who were ready to quit, was a referral made?
8. Regardless of readiness to quit, were youth given or told about resources that are available to learn more about the hazards of tobacco and nicotine use?
9. Regardless of readiness to quit, was youth given/told about resources to quit should s/he decide to do so?
10. Was parental tobacco use assessed?
11. Were parent(s) asked about?
  - a. Smoke free home
  - b. smoke free car
  - c. If anyone caring for the child smokes
12. If parent(s) smokes or uses nicotine products in the home or car, was s/he advised to quit smoking?
13. If parent(s) smokes, was s/he referred to smoking cessation programs?
14. If parent(s) smokes was s/he told about educational resources on the influence of parental smoking on the child/youth?

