#### 4. Background:

Cigarette smoking remains the most preventable cause of death in the US and contributes significantly to the occurrence of chronic conditions. *Adolescents are a particularly vulnerable and important group to target for tobacco cessation.* Progression from occasional to daily smoking almost always occurs by age 26, an event that substantially increases the risk for chronic disease in adulthood. Moreover, there has been rapid growth in electronic or e-cigarette use and other non-cigarette tobacco products among youth, which may further increase their risk for transitioning to cigarette use and the development of other addictions.

*Primary Care Providers (PCPs) play a critical role in tobacco-related disease screening, counseling, and early intervention among youth.* There is an evidence base demonstrating that PCP brief interventions contribute to overall tobacco cessation and reduction. Yet there are significant gaps in screening and management of risk factors, counseling about e-cigarettes, parental counseling, and follow-up interventions to reduce tobacco and e-cigarette use in primary care.

We are proposing a pilot study to increase PCP capacity to follow evidence-based guidelines for tobacco and nicotine product screening and intervention among youth ages 11 through 17. We selected the 6As intervention for two primary reasons. First, the American Academy of Pediatrics (AAP) and the U.S. Preventive Services Task Force recommend their use. Second, the 6As strategy has an evidence base demonstrating that physician screening, advice, and referrals are effective in contributing to tobacco cessation among adolescents. The 6As are: (1) “Anticipate” (future use), (2) “Ask” (about tobacco use), (3) “Advise” (advise the patient to quit using tobacco), (4) “Assess” (the patient’s readiness to quit using tobacco), (5) “Assist” (by setting a quit date, providing materials on quitting tobacco, providing tobacco cessation medications, and referring the patient for additional services and/or counseling), and (6) “Arrange” (by re-contacting the patient after their quit date and arranging a follow-up visit). Consistent with AAP recommendations, we will include screening for e-cigarette, cigars, chewing tobacco, and hookah use.

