Despite national recommendations, compliance with the 6As and other PCP office-based best practices are low. The majority of pediatricians advise patients who smoke to quit (81%) but only one-third discuss cessation strategies, and less than 20% make referrals to the quitline or other cessation programs. Facilitators to carrying out the 6As and other best practices in primary care include: incorporation of cues into electronic health records (EHRs); use of short screening tools to identify those at risk for initiating tobacco use as well as current tobacco users; development of patient registries to track outcomes and to facilitate implementation of mHealth applications focused on tobacco cessation; and training of clinicians and office staff on cessation counseling.

The primary purpose of our study is to conduct a pilot, practice-based intervention focused on increasing adherence to the 6As for youth ages 11 through 17 years. We also will incorporate AAP best practice recommendations to screen and counsel parents.

Secondarily, we want to better understand the effects of the practice intervention on enhancing practice capacity to adopt and sustain new interventions in the future. The systematic uptake of evidence-based practices (EBP) into primary care is influenced by multiple organizational characteristics including practice leadership, ability to adopt new interventions (capacity for change) and sustain them (adaptive reserve); HIT availability, and clinician self-efficacy around the particular EBP. Therefore, we will measure practice characteristics including practice capacity for change, adaptive reserve, and HIT capabilities and clinician self-efficacy around the 6As at baseline and at 3 months post intervention.

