The duration of the study participation for patients is variable. For those who do not smoke/use nicotine products or who smoke/use nicotine products but do not want to quit, the duration of the study is the baseline data collection (5 to 10 minutes for the youth and 5 to 10 minutes for the parent, inclusive of the informed consent), clinician screening and advising (2 to 5 minutes for the child and 2 to 5 minutes for the parent), and the follow-up telephone survey administered through the UF Survey Research Center (10 minutes) for a total estimated participation time of approximately 25 to 30 minutes. Adolescent participants will be offered another \$5 electronic Amazon gift card after completion of the follow-up telephone survey. For patients who smoke/use nicotine products and want to quit, their participation is an estimated 35 minutes for baseline and follow-up telephone survey data collection and provider discussion during the primary care visit. Practices can customize who conducts the screening and advising. For example, some practices assign that role to the nursing staff. In other practices, the clinician seeing the patient for the visit provides this screening and counseling himself or herself.

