### 6.2.5 Analysis Plan

Intervention effect on clinician adherence to the 6As: The primary outcome is clinician adherence to the 6As inclusive of tobacco and nicotine product use as collected in the medical records. During both the baseline and follow-up periods, we will request and review medical records to identify the following primary outcome measures: discussion of patient’s tobacco use, advice to quit, and discussion of parent’s tobacco use. Since this is a pre-post design with one intervention group and one control group, we will perform ANCOVA-type analyses assuming that the patients and providers are independent of each other. For each outcome, we will fit a logistic regression model in which the dependent variable is the post-intervention measure of the outcome. The main independent variables will be the pre-intervention measure of the outcome, group (binary: intervention vs. control), and pre-intervention measure by group interaction. In all models, we will also control for age, gender, and race, and clinic (multi-nominal: clinics 1-4). The model building process will follow guidelines provided by Hosmer and Lemeshow.

Intervention effect on practice characteristics: Practice characteristic data will be measured from the Change Process Capability Questionnaire and the Adaptive Reserve Questionnaire (Appendix B). We will collect the practice characteristic data twice, once at baseline and once at 9 months. Therefore, we will fit ANCOVA models for data analysis, assuming the practices are independent of each other. The characteristics include meeting frequency, clinician/staff performance evaluation, and planned communication. The primary predictor of interest is group (intervention vs. control). The model building process will follow guidelines provide by Muller and Fetterman. We will perform residual analysis to check the normality assumption of the models. We will perform box-cox transformation if there is a violation of the normality assumption.

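### The chart form cannot separate quit advice to users from prevention advice to non-users in baseline or control charts, so the primary advice-to-quit measure does not match its likely source item

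*Combined protocol and SAP*

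**What the plan says.** Section 6.2.5 takes the primary outcome, adherence to the 6As, from medical records and lists three measures: discussion of the patient's "tobacco use, advice to quit, and discussion of" the parent's tobacco use. It gives no Appendix E item number, numerator or denominator for any of them. Section 4 explains the Advise step as "advise the patient to quit using tobacco".

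Appendix E is the abstraction form. Its only item on advice given to the youth is item 5: "Was youth advised to not use: Cigarettes, Cigars/cigarillos, E-cigarettes, Hookah, or Smokeless tobacco products". The item carries no condition on use. The form's only wording about being advised to quit, item 12, concerns parents. Every item is answered under "Response options: Met? Yes or No".

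Other items do carry conditions. Items 2, 3 and 6 apply to youth who use (item 2: "If youth smokes or uses nicotine products, was youth asked about amount used"), item 7 to youth ready to quit ("For those who were ready to quit, was a referral made"), and items 12-14 to parents who use. Section 6.2.3 E says adherence is judged only through the steps that apply to the patient, but gives no coding rule.

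On who is in the charts, Section 6.2.2 describes participation that begins "For those who do not smoke/use nicotine products or who smoke/use nicotine products but do not want to quit" and includes screening and advising by the clinician. Baseline and control charts (6.2.3 E) are drawn by age and visit, not by tobacco use.

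**The concern.** Quitting presupposes use. If the advice-to-quit measure is filled from item 5, a 'Yes' for a never-user who was told not to start counts the same as a 'Yes' for a current user told to stop. Most youth are expected to be non-users, so a group difference would mainly describe prevention advice while being labelled as quit advice. Aim 2 seeks pilot data on adherence, and a later trial could be planned on the wrong quantity.

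The data as planned could not put this right afterwards. Use status that was never abstracted can be recovered only by a second chart review.

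A secondary worry concerns the conditional items. With only 'Yes' and 'No' printed, a 'No' may mean that the step was not done or that it did not apply.

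**Working it through.** **1. Matching measures to items.** Discussion of the patient's use corresponds to item 1, and discussion of the parent's use to item 10. Advice to quit has no exact counterpart for youth. Item 5 is the only candidate.

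**2. Can users be identified from the planned data?**
- Item 1 records that the youth was asked, and item 10 that parental use was assessed. Neither records the answer.
- A 'Yes' on item 2, 3 or 6 reveals a user, but only where the clinician went further, so these items cannot supply a denominator.
- The Y-TNPQ is given in the intervention groups only (6.2.3 C). It covers neither baseline charts nor control charts.
- Appendix F question 6 has a code for non-users, but it is a telephone report after a study visit. It cannot reach baseline charts from the six months before the study, and nothing links it to the consecutive control charts.

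**3. User share for the illustration.** Section 6.2.2 gives 11% e-cigarette use among high school students and about 218 screened to find 20 users. The 218 does not follow directly: 20/0.11 = 181.8, or 182. An unstated 20% addition would match it (181.8 × 1.2 = 218.2). Section 6.2.3 C gives about 190 per practice. The implied shares are 20/218 = 9.17% and 20/190 = 10.53%. I use 9.17% to 11%, with 5% and 30% as assumed extremes, because the share using any product is not given. The point does not depend on the 218.

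**4. What drives item 5.** Let p be the share of users, u the share of users advised, and v the share of non-users advised. Then

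P(item 5 = Yes) = p·u + (1 − p)·v.

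| p | 10-point change in v: 10(1 − p) | 10-point change in u: 10p |
|---|---|---|
| 5% (assumed) | 9.5 | 0.5 |
| 9.17% | 9.08 | 0.92 |
| 10.53% | 8.95 | 1.05 |
| 11% | 8.9 | 1.1 |
| 30% (assumed) | 7.0 | 3.0 |

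At 9-11% use, non-users make up 89-91% of the charts.

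**5. A false contrast, as an example.** Take p = 11%, and u = 81% in both groups. The 81% is the Section 4 figure for pediatricians who advise smokers to quit, so it is a share of pediatricians used here only as an assumed rate. Assume v = 20% in one group and 50% in the other:
- 0.11 × 0.81 + 0.89 × 0.20 = 26.7%
- 0.11 × 0.81 + 0.89 × 0.50 = 53.4%

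Item 5 differs by about 27 points with no difference in quit advice. The documents give no rate for v, so this shows the mechanism and does not forecast a result.

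**6. Users available.** Per 75 unselected charts: 75 × 0.0917 = 6.9, 75 × 0.1053 = 7.9, 75 × 0.11 = 8.25, so about 7-8. The range is 3.75 to 22.5 at 5% and 30%. Section 6.2.3 E does not make clear whether 75 is per practice or in total. If per practice, a group of two practices would hold about 14-17 users. Intervention follow-up differs: participants' records are reviewed, and the target is 20 users per practice.

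**7. Conditional items.** At 11% users, if non-users are coded 'No' on item 6, its rate cannot exceed 11%. If they are coded 'Yes', it cannot fall below 89%.

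**The case against.** The strongest reply is that the plan never says item 5 is the advice-to-quit measure. Section 6.2.5 names no item, and Section 6.2.3 E limits adherence to applicable steps, so the intended denominator may be users only. This stands as far as it goes: the link is inferred. But no other youth-advice item exists, and the applicability phrase cannot be applied to charts in which use is not abstracted.

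Second, item 5 may be deliberate. Section 6.2.2 has non-users receive advising too, and advice not to use is a legitimate best practice. This also stands. It makes the fault a mismatch between label and item, with advising used in two senses, and not an error in asking the item of everyone.

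Third, the seven conditional items are not among the three named primary measures, and 6.2.5 specifies no rate for them. A reviewer might leave an item blank when its condition is unmet. Correct: the missing rule is in the text, but miscoding is only a possibility.

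Fourth, this is a pilot. That lowers the stakes for inference but not for measurement, since Aim 2 is to gather data on exactly this behaviour.

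**Conclusion.** The point holds in a limited form and should be fixed. One of three primary measures has no stated item or denominator, its likely source does not match its label, and the planned data cannot separate quit advice from prevention advice in baseline or control charts. At 9-11% users, item 5 responds about 9 points to a 10-point change in prevention advice and about 1 point to the same change in quit advice. Prevention advice still dominates at an assumed 30% users (7.0 against 3.0). These sizes assume that item 5 is the source and is read over all charts.

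Three stronger readings are tempting but not supported:
- A reader might infer that the plan commits to reporting non-users' prevention advice as quit advice. It does not say how the measure is built, so this is a likely outcome and not a stated one.
- A reader might infer that the 'Yes'/'No' coding of conditional items damages the primary measures. Items 1 and 10 are unconditional and unaffected, and the conditional items bear only on the wider 6As outcome.
- A reader might infer that item 5 would move opposite to quit advice. That needs a fall in prevention advice, for which the documents give no basis.

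Confidence is high for what the form says and lower for how the results would be distorted.

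**What to change.** Before the baseline chart review:

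1. Add fields to Appendix E, taken from the chart in every group and period: documented youth use and documented parent use (user / non-user / not documented), and readiness to quit (ready / not ready / not documented).
2. Split item 5 into advice to quit (documented users) and advice not to start (all others).
3. On items 2, 3, 6, 7 and 12-14, add two codes: 'not applicable' when the chart documents that the condition is absent, and 'condition not documented'. Report both counts by group and period. A single 'not applicable' code would leave undocumented cases mixed with steps not done.
4. In 6.2.5, label the all-charts item 5 measure as advised not to use or to quit. Report quit advice among documented users separately, as counts with exact intervals, beside the documented-user share by group and period.

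Do not make 'documented user and advised, over all charts' the primary measure. It equals p·u when all use is documented, so it varies with prevalence and documentation. A rise from 81% to 100% of users advised would move it only 19p = 1.7-2.1 points, the same as item 5. Where the 20-user rule in 6.2.2 ends accrual, its numerator in an intervention practice is largely fixed, and the measure tends to 20 divided by the number screened (20/218 = 9.2%, 20/190 = 10.5%).

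The cost is somewhat longer abstraction (the documents give no timing) and reviewer training on the new codes to the 98% agreement standard. The users-only figure will be imprecise: 6 of 7 has an exact 95% interval of 42.1-99.6%. It also depends on documentation that the intervention may increase, so it should stay descriptive.

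### Chart-review item 12 covers parents who use any nicotine product but credits only advice to quit smoking, and items 13 and 14 cover only parents who smoke

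*Combined protocol and SAP*

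**What the plan says.** Appendix E is the form used for the medical record review at baseline and follow-up. It describes the parent of interest in three ways.

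- Item 10 is general: "Was parental tobacco use assessed".
- Item 12 covers smoking or nicotine products and mentions place: "If parent(s) smokes or uses nicotine products in the home or car, was s/he advised to quit smoking".
- Items 13 and 14 cover smoking only: "If parent(s) smokes, was s/he referred to smoking cessation programs" and "If parent(s) smokes was s/he told about educational resources on the influence of parental smoking on the child/youth".

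The only responses on the form are Yes and No.

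The PBQ (Appendix D) identifies parents by past-30-day use, with no question about place. Question 3 covers smoked products: "In the past 30 days, have you smoked a cigarette, a cigar, a pipe, even one or two puffs". Question 4 covers smokeless tobacco and leaves out nicotine replacement products. Question 5 covers the rest: "In the past 30 days, have you used e-cigarettes, a hookah, or dissolvable tobacco, even one or two times".

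Two other forms in the protocol use broad wording. The clinician survey (Appendix A, question 5h) asks about advising parents who use any tobacco or nicotine product to stop. The youth telephone survey (Appendix F, question 9) asks whether the provider talked with a parent or family member about giving up smoking or nicotine products. Section 6.2.5 plans a concordance analysis between chart data and each outcome of that telephone survey.

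**The concern.** Item 12 is inconsistent within itself: the group it admits is wider than the act it credits. A clinician who advises a vaping parent to stop vaping has done what the item appears to be for, but the words on the form do not give credit for it. Items 13 and 14 then leave that parent out, so a referral or educational resource given to that parent earns no credit either.

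Two sets of results are at stake. The first is adherence to the parent best practices under Aim 2, where the advise, refer and educate rates would describe different groups of parents. The second is the Aim 3 concordance analysis. A youth can correctly report on the telephone that the provider discussed quitting nicotine products with the parent while the chart item reads No. Sensitivity, specificity, predictive values and kappa would all treat that as real disagreement.

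**Working it through.** The plan states no figure on this point, so there is none to reproduce. The check sets the wording side by side and follows each type of parent through the items on a literal reading. Every parent in the table is positive on PBQ questions 3 to 5.

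| Parent | Does item 12 apply? | Item 12 if advised to stop own product | Do items 13 and 14 apply? |
|---|---|---|---|
| Smokes, in home or car | Yes | Yes | Yes |
| Smokes, elsewhere only | Depends on the reading | Yes, where it applies | Yes |
| Only vapes or uses smokeless, in home or car | Yes | No | No |
| Only vapes or uses smokeless, elsewhere only | No | Not eligible | No |

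In the second row, the place qualifier may attach to both verbs in item 12 or only to the use of nicotine products. The parent is outside item 12 on the first reading and inside it on the second. Where the table shows that an item does not apply, the form offers only No or a blank.

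Item 12 also does not exclude nicotine replacement, which PBQ question 4 does. Read literally, a parent using a patch in the home could be eligible.

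**Size, for illustration only.** Let t be the true rate at which item-12-eligible parents are advised to stop their own product, taken as equal for all products. Let v be the share of those parents who use only non-smoked products. The documents give neither value, so both are assumed. On literal coding the observed rate is t × (1 − v).

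| t | v = 0.10 | v = 0.20 | v = 0.30 | v = 0.40 |
|---|---|---|---|---|
| 0.80 | 0.72 | 0.64 | 0.56 | 0.48 |
| 0.50 | 0.45 | 0.40 | 0.35 | 0.30 |

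**Effect on concordance.** Suppose item 12 is compared with telephone question 9, and youth recall and charting are both perfect. Wording alone then makes a share t × v of pairs disagree. With t = 0.80 and v = 0.20:

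- disagreement = 0.80 × 0.20 = 0.16, so observed agreement = 0.84;
- chance agreement = 0.64 × 0.80 + 0.36 × 0.20 = 0.512 + 0.072 = 0.584;
- kappa = (0.84 − 0.584) / (1 − 0.584) = 0.256 / 0.416 = 0.62, where matched wording would give 1.

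**The case against.** The strongest reply is that nothing obliges a reviewer to read item 12 literally. Section 6.2.3 E uses certified coders trained to 98% agreement, with a trainer available for questions during the review. A sensible trainer could rule that advice to stop vaping counts. That is fair, and it is why the claim is that correct advice can be scored No, not that it will be. But the agreement target secures consistency, not validity: two coders who both read the item literally agree perfectly. No written coding rule covers product or place, and the rule limiting review to applicable steps is attached to the 6As, not to the parent items.

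A second reply is that the smoking and place wording has a purpose. Parent screening is justified in Section 6.2.3 D by the child's exposure to tobacco smoke, item 11 asks about smoke-free home and car, and item 12 follows from it. This explains items 13 and 14 in part. It does not explain why item 12 admits nicotine products and then credits advice on smoking alone.

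A third reply is that the plan does not map chart items to telephone questions, and question 9 also covers other family members, so some disagreement would remain after any rewording. That stands. The product mismatch is the part that can be removed at almost no cost.

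A reader might also infer that the intervention arm is penalised, since the PBQ is used only in intervention practices and may bring more non-cigarette users to light there. That is plausible, but the documents give no basis for saying how many such parents would be charted in either arm.

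**Conclusion.** The mismatch in item 12 and the differing denominators of items 12 to 14 are plain from the forms. They can understate parent advice, drop some parents from the referral and education items, and create artificial disagreement in the concordance analysis. The size cannot be stated: every figure in the working rests on assumed values of t and v, on literal coding and, for kappa, on perfect recall and charting.

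Three stronger readings are tempting but not supported.

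- **The primary outcome is affected.** Section 6.2.5 names discussion of the patient's tobacco use, advice to quit, and discussion of the parent's tobacco use. The last is closest to items 10 and 11, and the Advise step of the 6As concerns the patient. The plan does not map measures to items, so an effect is not shown.
- **Youth who use only e-cigarettes drop out of the Assess step.** Item 2 begins "If youth smokes or uses nicotine products, was youth asked about amount used", while item 6 reads "For those who smoke or use tobacco products was youth asked if they were ready to quit". The wording differs, but the youth questionnaire (Appendix C, questions 1 and 2) and PBQ question 1 both class e-cigarettes as tobacco products. On the documents' own usage these youth stay eligible for item 6.
- **Parents who smoke only outdoors go uncounted.** They leave item 12 on one of two readings, and they remain in items 13 and 14.

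**What to change.** Before abstraction starts, revise Appendix E as follows.

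1. Give items 12 to 14 one condition that matches PBQ questions 3 to 5: the parent uses any tobacco or nicotine product, including e-cigarettes and excluding nicotine replacement.
2. Word the act in item 12 as advice to stop the product or products used.
3. Keep home and car exposure in item 11 only.
4. Add a not-applicable response.
5. Use the same form in both arms at baseline and follow-up.

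Aligning item 6 with items 2 and 3 is an optional consistency edit.

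The cost is the rewording of three items, one added response option and a short briefing of the reviewers. No new source data are needed. The drawback is that items 13 and 14 become broader than smoke exposure. Recording the product used on the form deals with this, because results for smoking parents can then still be shown separately.
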